### 2.7.3 Vital signs

The summary of vital signs will only include on treatment data, which are defined as those vital sign measurements after the first dose of study treatment and on or before last dose + 84 days.

[figure not shown]
Analysis in vital sign measurement using descriptive summary statistics for the change from baseline for each post-baseline visit will be performed. These descriptive summaries will be presented by vital sign and treatment group. Change from baseline will only be summarized for subjects with both baseline and post-baseline values and will be calculated as:

$$\text{change from baseline} = \text{post-baseline value} - \text{baseline value}$$

The number and percentage of subjects with newly occurring notable vital signs will be presented. Criteria for notable vital sign abnormalities are provided in [Table 2-7](#) below.

**Table 2-7 Criteria for notable vital sign abnormalities**

Vital sign (unit)	Notable abnormalities
Systolic blood pressure (mmHg)	$\geq 140 \text{ mmHg}$ or $< 90 \text{ mmHg}$
Diastolic blood pressure (mmHg)	$\geq 90 \text{ mmHg}$ or $< 60 \text{ mmHg}$
Pulse (bpm)	$> 100 \text{ bpm}$ or $< 60 \text{ bpm}$

## 2.11 Interim analysis

The 16-weeks has already been performed after all patients completed the assessment for the primary and key secondary variables.

## 3 Sample size calculation

An overall type I error (2-sided) 5% will be used to control type I error. Since one i.v. regimen will be tested versus placebo with respect to the primary endpoint (ACR50 response at Week 16), the type-I-error is 5% two-sided for comparison. The total sample size of 190 subjects per each group is deemed appropriate to achieve adequate power for the primary and secondary endpoints for this study.

### 3.1.1 Primary endpoint(s)

Analysis of a phase III study (FUTURE 5) showed a placebo response rate of 8.1%, secukinumab 150 mg with SC loading response rate of 35.9%, and secukinumab 300 mg with SC loading response rate of 39.6% at week 16 for ACR50. Assuming that the response rate of i.v. regimen is between the response rates of secukinumab 150 mg with SC loading and 300 mg with SC loading, 190 subjects per group would yield approximately 99% power to detect a

treatment difference between 27.8% (based on the difference between secukinumab 150 mg with SC loading and Placebo) and 31.5% (based on the difference between secukinumab 300 mg with SC loading and Placebo) for the primary endpoint of ACR50 in the FAS population (two-sample Chi-Squared Test, Nquery 7.0).

**Table 3-1 Summary of power for binary primary endpoint**

Endpoint (Week 16)	Placebo Response Rate	Secukinumab with 150 mg SC loading		Secukinumab with 300 mg SC loading	
ACR50	8.1%	Response Rate	Power N=190/arm	Response Rate	Power N=190/arm
		35.9%	99%	39.6%	99%

### 3.1.2 Secondary endpoint(s)

A summary of the assumptions and power for the primary and secondary efficacy parameters using the FUTURE5 study week 16 data is shown in the [Table 3-2](#) for binary endpoints and [Table 3-3](#) for continuous endpoints.

**Table 3-2 Summary of power for binary secondary endpoints**

Endpoint (Week 16)	Placebo Response Rate	Secukinumab with 150 mg SC Loading		Secukinumab with 300 mg SC Loading	
		Response Rate	Power N=190/arm	Response Rate	Power N=190/arm
ACR50	8.1%	35.9%	99%	39.6%	99%
MDA	7.8%	27.7%	99%	32.4%	99%
PASI90	9.3%	36.8%	99%	53.6%	99%
ACR20	27.4%	55.5%	99%	62.6%	99%
Resolution of Enthesitis	35.4%	54.6%	80%	55.7%	84%
Resolution of Dactylitis	32.3%	57.5%	83%	65.9%	98%

**Table 3-3 Summary of power for continuous secondary endpoints**

Endpoint (Week 16)	Placebo Mean change from baseline	Secukinumab with 150 mg SC Loading			Secukinumab with 300 mg SC Loading		
		Mean change from baseline	Common standard deviation	Power N=190/ arm	Mean change from baseline	Common standard deviation	Power N=190/ arm
HAQ-DI	-0.21	-0.44	0.507	99%	-0.55	0.508	99%

mNAPSI	-2.49	-9.31	9.503	99%	-9.18	9.503	99%
FACIT	1.98	6.18	9.303	99%	6.8	9.303	99%
SF36-PCS	1.83	6.3	7.304	99%	7.62	7.33	99%
PASDAS	-0.91	-2.02	1.359	99%	-2.37	1.361	99%

## 4 Appendix

## 4.1 Visit Windows

### 4.1.1 Visit windows

When visit windows are used, all visits will be re-aligned, i.e., they will be mapped into one of the visit windows. E.g., if the *Week 4* visit of a subject is delayed and occurs on Day 46 instead of on Day 29, say, it will be re-aligned to visit window *Week 8*. In the case of major deviations from the visit schedule, or due to unscheduled visits, several assessments of a subject may fall in a particular visit window (either scheduled or unscheduled). Statistical approaches to handle multiple assessments in a given visit window are specified in [Table 4-2](#).

For lab/vital signs, follow-up (F/U) visit is excluded from analysis visit mapping window. Only assessments that come as F/U nominal visit will be directly assigned as analysis F/U visit. Other assessments that are beyond the last on-treatment visit window or after nominal F/U visit date won't be mapped to any analysis visit. F/U visit will not be included in the summary tables by visit.

Of note, subjects are allowed to have gaps in visits. All data collected will be displayed in listings.

**Table 4-1** Analysis visit windows

Analysis Visit	Target Day	Group 1	Group 2	Group 3	Group 4	Group 5	Group 6	Group 7	Group 8	Group 9	Group 10
Baseline	1	≤1*		≤1*	≤1*	≤1*	≤1*		≤1*	≤1*	
Week 4	29	2 – 43		2 – 43	2 – 43	2 – 43	2 – 43		2 – 43		
Week 8	57	44 – 71		44 – 71	44 – 71	44 – 71	44 – 71		44 – 71	2 – 71	
Week 12	85	72 – 99		72 – 99	72 – 99	72 – 99	72 – 99		72 – 99		
Week 16	113	100 – 127		100 – 141	100 – 141	100 – 141	100 – 127		100 – 141	72 – 141	
Week 20	141	128 – 155					128 – 155				
Week 24	169	156 – 183		142 – 183	142 – 183	142 – 197	156 – 183		142 – 197	142 – 291	
Week 25	176										

Analysis Visit	Target Day	Group 1	Group 2	Group 3	Group 4	Group 5	Group 6	Group 7	Group 8	Group 9	Group 10
Week 28	197	184 – 211		184 – 239	184 – 281		184 – 211				
Week 32	225	212 – 239				198 – 253	212 – 239		198 – 253		
Week 36	253	240 – 267					240 – 267				
Week 40	281	268 – 295		240 – 323		254 – 309	268 – 295		254 – 347		
Week 44	309	296 – 323					296 – 323				
Week 48	337	324 – 351				310 – 351	324 – 351				
Week 52	365	352 – 439		324 – 439	282 – 439	352 – 439	352 – 410		347 – 439	292 – 439	
Week 60	421						411 – 439				

\* The first administration of randomized study treatment (first dose) is defined as Day 1.

Group1: [REDACTED] ESR, High sensitivity C-Reactive protein, [REDACTED] Vital sign

Group2: [REDACTED]

Group3: Hematology, blood chemistry, [REDACTED]

Group 4: [REDACTED] SF-36 v2, FACIT, [REDACTED]

Group 5: LEI, LDI, PASI, [REDACTED] BSA assessment, Patient's global assessment of psoriasis and arthritis disease activity (VAS), IGA

Group 6: Urine pregnancy test

Group 7: [REDACTED]

Group 8: mNAPSI, Physician's global assessment of fingernail disease severity (VAS)

Group 9: urinalysis, Lipids

Group 10: [REDACTED]

The following rules are used to determine the window for an applicable visit post baseline: "Lower limit" = "upper limit of prior applicable visit" + 1. "Upper limit" = "target day of current visit" + integer part of ("target day of next applicable visit" – "target day of current visit")/2. Lower limit of the first applicable visit is always Day 2. Day 1 is the date of the first dose of randomized study treatment

The mapping described above applies to all visits (not just scheduled visits). Repeat and/or unscheduled visits (which will be numbered in the database according to new NCDS standards) will be mapped for analysis purposes in the same way as scheduled visits. This leaves the possibility, then, for multiple measurements within an analysis window. The following

conventions will be used to determine the appropriate measurement to be summarized in the event of multiple measurements within a visit window.

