### Psoriatic Arthritis Disease Activity Score (PASDAS)

PASDAS is a new composite measure developed to access disease activity in Psoriasis (GRACE Project) ([Helliwell 2012](#)). It is calculated by utilizing seven measures; the seven components are: Patient reported measures (excluding mental component summary score (MCS) of the medical outcomes survey Short Form-36 (SF-36-PCS)), skin, peripheral joint counts (Tender and Swollen joint counts), Dactylitis (LDI), Enthesitis (LEI), acute phase response (CRP) and Patient & Physician global VAS scores.

$$\begin{aligned} \text{PASDAS} = & (((0.18 \times \sqrt{\text{Physician global VAS}}) \\ & + (0.159 \times \sqrt{\text{Patient global VAS}}) \\ & - (0.253 \times \sqrt{\text{SF36-PCS}}) \\ & + (0.101 \times \ln(\text{Swollen joint count} + 1)) \\ & + (0.048 \times \ln(\text{Tender joint count} + 1)) \\ & + (0.23 \times \ln(\text{Leeds Enthesitis Count} + 1)) \\ & + (0.377 \times \ln(\text{Dactylitis count} + 1)) \\ & + (0.102 \times \ln(\text{CRP} + 1)) + 2) * 1.5. \end{aligned}$$

If any component measurement is missing, PASDAS will be missing. The patient global VAS defined in the PASDAS score is “VAS for PASDAS assessment” which measures patient’s global assessment of PSORIASIS and ARTHRITIS disease activity. The Physician global VAS is the Physician’s global assessment of PsA disease activity. Tender Dactylitis count is from “Leeds Dactylitis Instrument” CRF page with “Was dactylitis present?” = “Yes” and “Tender/non-tender” = “Tender”.

66-swollen / 68-tender joint counts for PASDAS assessment:

There are only 66 swollen and 68 tender joint counts which will be used for PASDAS assessment. That is the 10 joints in CRF: CMC1, DIP2 (FOOT), DIP3 (FOOT), DIP4 (FOOT), and (DIP5 (FOOT) both left and right, should not be counted in the swollen/tender joint count in PASDAS formula.

If the number of joints for which data were available (e.g., T) is less than 66/68 for the swollen/tender joint assessment, the number of swollen/tender joints (e.g., t) will be scaled up proportionately (i.e.,  $66*t/T$  or  $68*t/T$  for swollen or tender joint count).

[figure not shown]

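### SAP Table 4-1: the Week 40 and Week 52 windows for mNAPSI break the SAP's own rule and share Day 347; the order of deriving and windowing PASDAS should also be stated

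*SAP*

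**What the plan says.** SAP section 4.1.1 assigns windows by parameter group in Table 4-1. It intends one window per visit: "When visit windows are used, all visits will be re-aligned, i.e., they will be mapped into one of the visit windows". The formula stands below the table ("The following rules are used to determine the window for an applicable visit post baseline"). The upper limit is the target day of the current visit plus "integer part of ('target day of next applicable visit' – 'target day of current visit')/2". The lower limit is the previous upper limit plus one, and the first applicable visit opens on Day 2.

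The nail measures are listed as "Group 8: mNAPSI, Physician's global assessment of fingernail disease severity (VAS"). The Group 8 column has windows for Weeks 4, 8, 12, 16, 24, 32, 40 and 52. The last two are printed as 254–347 and 347–439. Where several post-baseline efficacy values fall in one window, Table 4-2 takes the value closest to the target day.

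The visible inputs to PASDAS are spread over three groups. CRP is in Group 1 ("ESR, High sensitivity C-Reactive protein"), SF-36 is in Group 4, and LEI, LDI and the psoriasis-and-arthritis patient VAS are in Group 5. The PASDAS part of SAP 2.5.1 adds: "If any component measurement is missing, PASDAS will be missing". PASDAS itself, the joint counts and the physician's global VAS appear in no visible group. Groups 2, 7 and 10 are wholly redacted, and several other group lists are partly redacted.

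SAP section 1 limits this document to the final database lock. The Week 16 analyses and the testing hierarchy are not repeated.

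**The concern.** A window table is programmed as printed. If it contradicts the formula beside it, the programmer must choose between them. If two windows share a day, the table cannot be executed for that day. For mNAPSI, the days in dispute are those on which a subject who stops late in Period 2 has a final assessment. Under the printed cells, that value is labelled Week 40 although it lies closer to Week 52.

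For PASDAS, the question is the order of operations. The score needs every component. If each component is first assigned to a visit through its own group's windows, components taken on one day can receive different visit labels. The score would then be missing although nothing was missed. The subjects exposed to this are mainly those who discontinue, and their data matter most for missing-data bias.

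**Working it through.** **Check of the formula.** Target day = 7 × week + 1, and each group's own visits are the applicable visits. The formula reproduces every printed limit in Groups 1, 3, 4 and 5, apart from the last upper limit of 439, for which there is no next visit. It also reproduces Group 8 up to Week 32:

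- Week 16: 113 + (169 − 113)/2 = 141 (printed 141)
- Week 24: 169 + (225 − 169)/2 = 197 (printed 197)
- Week 32: 225 + (281 − 225)/2 = 253 (printed 253)

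**Group 8, Week 40.** 281 + (365 − 281)/2 = 281 + 42 = 323. The printed limit is 347, which is 24 days later. Week 52 should therefore open on Day 324.

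- No other choice of next visit gives 347: Week 44 gives 295, Week 48 gives 309 and Week 60 gives 351.
- Group 3 has the same Week 40 and Week 52 pair and prints 323 and 324.
- Days 324–346 (23 days) go to Week 40 where the formula gives Week 52. Day 347 is in both.

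**An example.** Protocol sections 8 and 9.1.1 bring a discontinuing subject back 4 weeks after the last dose. After a last dose at Week 44, that visit falls at Week 48, Day 337. This is 28 days from the Week 52 target (365 − 337) and 56 days from the Week 40 target (337 − 281). Table 4-1 nevertheless labels it Week 40. If the subject also has a Day 281 value, the closest-to-target rule selects that one, and the Day 337 value enters no by-visit summary.

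**Other columns against the same formula.**

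| Group | Window | Formula upper limit | Printed |
|---|---|---|---|
| 6 (urine pregnancy test) | Week 52 | 365 + 28 = 393 | 410 |
| 9 (urinalysis, lipids) | Week 8 | 57 + 28 = 85 | 71 |
| 9 (urinalysis, lipids) | Week 24 | 169 + 98 = 267 | 291 |

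None of these creates an overlap.

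**PASDAS component windows.** Each day from 2 to 439 was mapped through Groups 1, 4 and 5. The three agree on Days 2–127, 156–183 and 352–439. They disagree on Days 128–155 (28 days) and 184–351 (168 days), together 196 of 438 days. They agree on every shared target day (29, 57, 85, 113, 169, 365).

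The end-of-treatment visits of Period 2 discontinuers, exactly on schedule, map as follows:

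| Last dose | Visit day | CRP (Group 1) | SF-36 (Group 4) | LEI, LDI, VAS (Group 5) |
|---|---|---|---|---|
| Week 16 | 141 | Week 20 | Week 16 | Week 16 |
| Week 20 | 169 | Week 24 | Week 24 | Week 24 |
| Week 24 | 197 | Week 28 | Week 28 | Week 24 |
| Week 28 | 225 | Week 32 | Week 28 | Week 32 |
| Week 32 | 253 | Week 36 | Week 28 | Week 32 |
| Week 36 | 281 | Week 40 | Week 28 | Week 40 |
| Week 40 | 309 | Week 44 | Week 52 | Week 40 |
| Week 44 | 337 | Week 48 | Week 52 | Week 48 |

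Seven of the eight are split. If components are windowed first, the complete set from such a visit gives no PASDAS for that visit under the missing-component rule.

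**The case against.** The Group 8 discrepancy itself has no good defence, but its reach is small. The scheduled Week 52 visit (Day 365) would have to be at least 18 days early to touch it, and Group 8 has no visit between Days 281 and 365. A reader might infer that final mNAPSI visits in general are put in the wrong week. That is not so: on-schedule Week 40 and Week 52 visits are labelled correctly.

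On PASDAS, several stronger readings are tempting, and the documents do not support them.

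- That complete PASDAS data are discarded. This follows only if components are windowed before derivation, and the visible SAP does not state the order. The missing-component rule speaks of measurements, not windowed values. PASDAS may also have its own entry in a redacted group.
- That scores are built from different dates. A shifted visit alone gives a missing score; mixing also needs a repeated or partly missing component.
- That the Week 16 comparison is affected, through a Week 16 visit on Days 128–141. Such a visit would be at least 15 days late, and no Week 16 test is run under this SAP.
- That MDA and ACR share the problem. The groups holding several of their components are not visible, so no split can be shown.

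It is also fair to say that much of the 196-day count falls where no complete PASDAS set is scheduled. The count describes windows, not subjects, and the documents do not say how many visits fall there. What stands is that discontinuers' end-of-treatment visits fall in these gaps by design, without any scheduling deviation.

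**Conclusion.** The Group 8 error is established from the printed table and formula alone, and no redaction bears on it. The Week 40 upper limit is 24 days too late, 23 days are assigned to the wrong visit, and one day is assigned to two. The consequence is limited to early-termination or off-schedule nail assessments in the long-term summaries. No confirmatory result depends on it.

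The PASDAS point is secondary and conditional. The component windows do disagree, but a score is lost only if windowing comes first and no redacted text settles the matter. The supportable conclusion is that the order is not visibly specified and should be.

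**What to change.** Change two cells of Table 4-1 for Group 8: Week 40 to 254–323 and Week 52 to 324–439. Check every other column against the formula. For Groups 6 and 9, either correct the limits or state that the departure is intended.

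Unless redacted text already does so, add one sentence: PASDAS is derived from components of the same visit and the score is then windowed once, with a named window set. The set must be named because Groups 4 and 5 still differ; Day 300, for example, is Week 52 in one and Week 40 in the other. One option is to use only the visits common to Groups 1, 4 and 5 (Weeks 4, 8, 12, 16, 24 and 52). The SAP's formula then gives 2–43, 44–71, 72–99, 100–141, 142–267 and 268–439. The last window is wide, so the choice should be deliberate.

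The cost is a few table cells, one sentence and possibly a change in programming order. No new data are needed.

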**Table 4-2 Rules for flagging variables**

Timing of measurement	Type of data	Rule
Baseline	All data	
The last non-missing measurement made prior to or on the date of administration of the first dose of study treatment (the reference start date / Day 1). If a patient did not receive any dose of study treatment then the randomization date will be used. Only date part is considered if just one assessment on Day 1.
 
If there are multiple assessments on Day 1, following rules will apply:
 
If assessment time exists, select the last available measurement prior to reference start date/time considering time; if no measurement prior to reference start date/time considering time, select the earliest measurement post reference start date/time considering time .
 
If assessment time does not exist, select the available measurement from the lowest CRF visit number.
 
For X-ray, a baseline value is the last measurement prior to dosing if available. Otherwise, take the first value within 30 days post dosing.
 
For MRI, a baseline value is the last measurement prior to dosing if available. Otherwise, take the first value within 7 days post dosing.

Post-baseline efficacy	All data	
For visits without switch of treatment in the window, the measurement closest to the target will be used. In the event two measurements are taken equally apart (e.g. 1 before target date and 1 after) the first one will be used.
 
Cases where the same parameter is recorded more than once on the same date will be handled as follows:
 
If time of completion exists the earliest measurement will be used;
 
If time does not exist the measurement from the lowest CRF visit number will be used.

Timing of measurement	Type of data	Rule
Post-baseline safety	Summary visit information (e.g. lab, etc.)	For visits without switch of treatment in the window, the measurement closest to the target will be used. In the event two measurements are taken equally apart (e.g. 1 before target date and 1 after) the first one will be used. Cases where the same parameter is recorded more than once on the same date will be handled as follows: If time of completion exists the earliest measurement will be used; If time does not exist the measurement from the lowest CRF visit number will be used.
Post-baseline safety	Notable abnormalities (e.g. lab)	The most extreme measurement in the window will be used. Note this means a patient can have a notably high and notably low measurement within a window.

## 4.2 Detailed on implementation of statistical methodology and assumptions

### 4.2.1 Analysis of continuous data

#### 4.2.1.1 Summary statistics for continuous data

Summary statistics (including N, mean, standard deviation, minimum, lower quartile, median, upper quartile, maximum) will be provided for continuous data by visit and treatment group.

#### 4.2.1.2 Mixed-effects repeated measures model

Endpoints with continuous data type expected to be normally distributed (e.g, [REDACTED]) will be analyzed using a mixed-effects repeated measures model (MMRM) with stratification factor and analysis visit as factors; and weight, baseline value, baseline by visit interaction as covariates. An unstructured correlation matrix will be used thus allowing adjustment for correlations between time points within subjects.

SAS code for mixed model:

```
proc mixed data=aaa;  
class USUBJID AVISITN STRATA;  
model CHG= STRATA AVISITN WEIGHT BASE BASE*AVISITN  
/ s ddfm=kr;  
lsmeans AVISITN / diff cl;
```

repeated AVISITN / type=un subject=USUBJID;

Run;

In case the MMRM model does not converge the following sequential steps will be used:

1. change ddfm=kr to ddfm=bw. If still no convergence, perform step 2.
2. change type=un to type=cs. If still no convergence, perform step 3.
3. remove covariates in the following order until convergence: WEIGHT, BASE\*AVISITN, STRATA.

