6.3.2 Treatment assignment, randomization

At BSL, all eligible subjects will be randomized via Interactive Response Technology (IRT) to one of the treatment arms. The investigator or his/her delegate will contact the IRT after confirming that the subject fulfills all the inclusion/exclusion criteria. The IRT will assign a randomization number to the subject, which will be used to link the subject to a treatment arm and will specify a unique medication number for the first package of investigational treatment

to be dispensed to the subject. The randomization number will not be communicated to any of the site staff.

The randomization numbers will be generated using the following procedure to ensure that treatment assignment is unbiased and concealed from subjects and investigator staff. A subject randomization list will be produced by the IRT provider using a validated system that automates the random assignment of subject numbers to randomization numbers. These randomization numbers are linked to the different treatment arms, which in turn are linked to medication numbers. A separate medication list will be produced by or under the responsibility of Novartis Global Clinical Supplies using a validated system that automates the random assignment of medication numbers to packs containing the investigational drug(s).

The subjects will be stratified at randomization according to either TNF -IR or TNF- naïve subjects. Up to 25% of randomized subjects will be TNF- IR to ensure a representative subject population for the assessment of efficacy and safety.

The randomization scheme for subjects will be reviewed and approved by a member of the Randomization Office.

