12.4.2 Statistical model, hypothesis, and method of analysis

The statistical hypothesis for ACR50 being tested is that there is no difference in the proportion of subjects fulfilling the ACR50 criteria at Week 16 in i.v. secukinumab vs. placebo regimen.

Let p_j denote the proportion of ACR50 responders at Week 16 for treatment regimens j , $j=0, 1$ where

- 0 corresponds to placebo regimen,
- 1 corresponds to i.v. regimen,

In statistical terms, $H_0: p_1 = p_0$, $H_{A1}: p_1 \neq p_0$, for the i.v. secukinumab regimen, i.e.

H_1 : The i.v. secukinumab. regimen is not different to placebo regimen with respect to signs and symptoms (ACR50 response) at Week 16

The primary endpoint of ACR50 at Week 16 in the FAS will be evaluated using a logistic regression with treatment and randomization stratum (TNF α status –naïve or IR) as factors and weight as a covariate. Difference in marginal response proportions will be computed for comparisons of i.v. secukinumab vs. placebo regimen utilizing the logistic regression model fitted.

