### 1.1 Study Design

This multicenter study uses a randomized, double-blind, placebo-controlled, parallel-group design to study the efficacy, safety and tolerability of treatment with intravenous secukinumab in patients with active PsA.

The study population comprises approximately 380 patients with active PsA, despite current or previous NSAID, DMARD and / or TNF inhibitor therapy or intolerance to these therapies.

At baseline, patients will be randomized to one of the two treatment groups in a 1:1 randomization:

- **Group 1:** approximately 190 patients; These patients will receive secukinumab 6 mg/kg i.v. at Baseline (BSL), followed by the administration of secukinumab 3 mg/kg i.v. every four weeks starting at Week 4.
- **Group 2:** approximately 190 patients; These patients will receive i.v. placebo at BSL, Weeks 4, 8, and 12, followed by the administration of secukinumab 3 mg/kg i.v. every four weeks starting at Week 16.

This study will consist of 4 periods: a screening period (up to 10 weeks), treatment period 1 (total duration of 16 weeks) and treatment period 2 (total duration of 36 weeks) followed by a safety follow up period of 8 weeks after the end of treatment visit (i.e., Week 52).

To ensure a balance across both arms, patients previously treated with TNF-inhibitors will be stratified at randomization. No more than 25% of previously treated TNF-inhibitor patients will be enrolled in the study, with this cutoff applied to each group at randomization (no more than 48 patients per group).

Because PsA is considered a chronic disease with no ‘true’ and lasting placebo response, all patients, including those on placebo, will switch to open-label i.v. secukinumab at Week 16. However, all patients and investigators/ site staff will remain blinded to the original randomized treatment group assignment (i.v. secukinumab treatment or placebo).

[figure not shown]
An end of treatment visit (Week 52) will be done 4 weeks after last study treatment administration, and a post treatment follow-up visit (Week 60) is to be done 8 weeks after end of the treatment visit for all subjects (regardless of whether they complete the entire study as planned or discontinue prematurely).

All intravenous infusions will be performed at the study site and site personnel will administer the infusions to subjects.

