### 2.2.1 Subgroup of Interest

The primary endpoint(s) and secondary endpoints will be evaluated for TNF-alpha inhibitor status. The primary and some secondary endpoints will be also evaluated for MTX status.

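### The final-lock MMRM's LS-means weight TNF-IR and TNF-naive patients 50:50, although TNF-IR is capped at 25%; take them at the enrolled mix or justify the equal weights

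*SAP*

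**What the plan says.** SAP Section 1 limits this plan to long-term efficacy and safety at the final database lock; Week 16 analyses and the testing hierarchy are not repeated. For continuous endpoints, SAP 4.2.1.2 prints the MMRM code. The stratum is a class variable ("class USUBJID AVISITN STRATA") and enters as a main effect, with no treatment or sequence term ("model CHG= STRATA AVISITN WEIGHT BASE BASE*AVISITN"). The covariance is unstructured ("repeated AVISITN / type=un subject=USUBJID"). Visit means are requested with "lsmeans AVISITN / diff cl". If the model does not converge, step 3 of the fallback removes covariates, STRATA last.

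The stratum has two levels. Protocol 6.3.2 states: "The subjects will be stratified at randomization according to either TNF -IR or TNF- naïve subjects". SAP 1.1 states: "No more than 25% of previously treated TNF-inhibitor patients will be enrolled in the study", and limits each group to 48 such patients.

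SAP 4.2.1.1 separately provides unadjusted means by visit and treatment group, and SAP 2.5.3 says that data after Week 16 are generally shown as observed cases.

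**The concern.** Without the OM (observed margins) option, PROC MIXED averages an LS-mean over the levels of any other class effect with equal weights. Patients who can make up at most about a quarter of the trial therefore receive half the weight.

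In a treatment contrast this would not matter, because a main-effect stratum term cancels. Here there is no treatment term, so the LS-means themselves are absolute visit means and nothing cancels. The same code evaluates weight and baseline at their observed means, so the adjusted means combine an observed covariate profile with a TNF mix that enrolment rules out. The unadjusted visit means and the multiply imputed ACR50 rates (SAP 4.2.3) carry the actual mix. One report would then hold figures for two populations without saying so.

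**Working it through.** **Inputs from the documents**
- Cap: 25% TNF-IR, at most 48 per group (SAP 1.1; Protocol 6.3.2). Group size: 190 (SAP 3).
- HAQ-DI, used only for scale: changes −0.21 and −0.44, SD 0.507 (SAP Table 3-3, 150 mg columns).
- Post-baseline visits: 7 or 13 (SAP Table 4-1, Groups 4 and 1).

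**Assumptions (not in the documents)**
- Exchangeable within-patient correlation ρ of 0.3 to 0.9, complete data, known covariance.
- An adjusted TNF-IR minus TNF-naive difference δ of size 0 to 0.3 HAQ-DI units, either sign.

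**1. The plan's own figures.** 0.25 × 190 = 47.5, rounded up to 48; 48/190 = 25.3%. Power for HAQ-DI with 190 per arm, difference 0.23, SD 0.507, two-sided 5% is 99.3%, in line with the stated 99%.

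**2. Shift in the mean.** Write the model mean at visit t as μ_t + wδ, where μ_t is the TNF-naive mean and w the weight on TNF-IR. The printed code uses w = 0.5; the enrolled mix has w = p. So

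LS-mean (printed code) − enrolled-mix mean = (0.5 − p) × δ.

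| TNF-IR share p | Shift | δ of size 0.1 | 0.2 | 0.3 |
|---|---|---|---|---|
| 25.3% (cap) | 0.247 δ | 0.025 | 0.049 | 0.074 |
| 20% | 0.30 δ | 0.03 | 0.06 | 0.09 |
| 10% | 0.40 δ | 0.04 | 0.08 | 0.12 |

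If δ = 0 the shift is zero at every share.

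**3. Standard error.** The stratum effect is common to all k visits, so its estimate gains from averaging over them. Relative to the enrolled-mix mean,

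SE ratio = √{1 + [(0.5 − p)² / (p(1 − p))] × f}, with f = (1 + (k − 1)ρ)/k.

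At the cap, (0.247)²/(0.253 × 0.747) = 0.324 from unrounded shares.
- One visit: f = 1, ratio √1.324 = 1.15.
- Seven visits, ρ = 0.5: f = 4/7, ratio √1.185 = 1.09.
- Thirteen visits, ρ = 0.3: f = 4.6/13, ratio √1.115 = 1.06.

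| TNF-IR share | 1 visit | 7 visits, ρ 0.3–0.9 | 13 visits, ρ 0.3–0.9 |
|---|---|---|---|
| 25.3% (cap) | 1.15 | 1.06–1.14 | 1.06–1.14 |
| 20% | 1.25 | 1.11–1.23 | 1.10–1.23 |
| 10% | 1.67 | 1.31–1.62 | 1.28–1.62 |

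A generalised least-squares calculation that includes weight, baseline and baseline-by-visit gives the same values. The ratio depends on the share and hardly at all on the number of patients, and equals 1 only at a 50% share.

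**4. Scale.** For 190 patients with SD 0.507 at the cap, the 95% half-width at the enrolled mix is 1.96 × 0.507/√190 = 0.072. With the printed code it is 0.083 for one visit (× 1.15) and 0.078 for seven visits with ρ = 0.5 (× 1.09).

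**5. What cancels.** STRATA has no interaction with visit, so wδ drops out of every visit-to-visit difference. It would also drop out of a between-sequence difference if a sequence term were added to this main-effects model with common margins.

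**The case against.** Equal-margin LS-means are the conventional default, and neither document promises observed margins for the MMRM, so no stated rule is broken. Unadjusted means with the enrolled mix are reported anyway. No test depends on the LS-means. The two weightings target different quantities, so the SE ratio is not purely lost efficiency. In the seven-visit HAQ-DI example the half-width grows by 0.078 − 0.072 = 0.006, against the 0.35-point HAQ-DI response threshold in SAP 2.5.1. The endpoint list in SAP 4.2.1.2 is redacted, so it is not visible which variables use this model.

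All of this stands, and it limits the reach and weight of the point. It does not supply a reason for 50:50. Nothing in either document chooses that target, while Protocol 4.1.1 and 6.3.2 justify the capped TNF-IR share as representative. The continuous estimand in Protocol 12.5.1 refers to the population set by the eligibility criteria, and Protocol 5.1 states the cap among them.

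A reader might also infer a conflict with the binary analysis, where "Difference in marginal response proportions will be computed for comparisons of i.v. secukinumab vs. placebo regimen", or with the subgroup results, since "The primary endpoint(s) and secondary endpoints will be evaluated for TNF-alpha inhibitor status". Neither inference is secure. The marginal-proportion analysis is the Week 16 logistic regression. The protocol's primary and secondary endpoints are Week 16 variables. SAP Section 1 says Week 16 analyses are not repeated.

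**Conclusion.** The point holds for the MMRM LS-means only. Each gives TNF-IR a weight of 0.50 although its share cannot exceed about 0.25, so that share is about doubled at the cap and more than doubled below it. The shift is (0.5 − share) × the adjusted stratum difference, about 0.25 of that difference at the cap. The SE is about 6–15% larger at the cap than for the enrolled-mix mean, given 1 to 13 visits and exchangeable correlation 0.3 to 0.9, and larger still at lower shares.

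Two stronger readings are tempting. One is that all long-term visit means describe a population that was not enrolled. The raw and observed-case means do not, and the LS-means would not either if the fallback removed STRATA. The other is that the results are pulled toward harder-to-treat patients. The documents give no difference in change between the strata; Protocol 4.2 says only that both s.c. regimens beat placebo whatever the TNF status. The size and sign of the shift are therefore unknown.

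Visit-to-visit and between-sequence differences and the Week 16 tests are unaffected. The change is inexpensive and worth making, but no tested conclusion depends on it.

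**What to change.** Change the request to `lsmeans AVISITN / om=<FAS margin data set> diff cl;`. The margin data set should hold one record per FAS subject per analysis visit, with all model variables: STRATA, AVISITN, WEIGHT and BASE. A file with one record per subject would lack AVISITN, which is in the model. Taking margins from the analysis records would let patients with more completed visits count for more. Code STRATA as in the model; SAP 2.2 analyses the FAS by actual anti-TNF status.

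Add one sentence to SAP 4.2.1.2: LS-means are computed at the FAS share of TNF-naive and TNF-IR patients, with the same margins for both sequences. If an equal-weight mix is the intended target, say so and give the reason.

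The cost is a small extra data set, one option and one sentence. No new data are needed and the differences listed above do not change. The downside is that these LS-means will differ slightly from any default-weight LS-means reported elsewhere.
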